9. STATISTICAL METHODOLOGY

9.1 General

Data listings will be provided for all data that is databased. Summary statistics and statistical analysis will only be presented for data where detailed in this SAP. For continuous data, summary statistics will include the arithmetic mean, arithmetic standard deviation (SD), median, min, max and N; for log-normal data (e.g. the PK parameters: AUCs and C_{max}) the geometric mean and geometric coefficient of variation (CV%) will also be presented. For categorical data, frequency count and percentages will be presented. Data listings will be provided for all patients up to the point of withdrawal, with any patients excluded from the relevant population highlighted. Summary statistics and statistical analyses will generally only be performed for patients included in the relevant analysis population. For the calculation of summary statistics and statistical analysis, unrounded data will be used.

Mean change from baseline is the mean of all individual patients' change from baseline values. Each individual change from baseline will be calculated by subtracting the individual patient's baseline value from the value at the timepoint. The individual patient's change from baseline values will be used to calculate the mean change from baseline using a SAS procedure such as Proc Univariate.

Data analysis will be performed using SAS[®] Version 9.4 or greater.

9.2 Demographics and Patient Disposition

Patient disposition will be listed. The demographic variables age, sex, race, ethnicity, country of enrolment, site ID, body weight, height, body mass index, screening HbA1c levels, fasting plasma glucose (Day 1, Predose for each cohort), duration of diabetes, and baseline vital signs (pulse rate and blood pressure, Day -1 for each cohort) will be summarized by treatment regimen, and listed.

9.3 Pharmacokinetic Assessment

9.3.1 Pharmacokinetic Analysis

Model-based analysis will be performed combined with data from other studies by Global PK/PD and Pharmacometrics group in Eli Lilly and Company. Details will be described in a separate analysis plan.

PK parameter estimates will be determined using non-compartmental procedures in validated software program (Phoenix WinNonlin Version 6.4 or later).

Plasma concentrations of LY3298176 will be used to determine the following PK parameters, when possible:

| Parameter | Units | Definition |
|-----------------|---------|---|
| AUC(0- τ) | ng.h/mL | area under the concentration versus time curve during one dosing interval (e.g. 168 hours) |
| C_{\max} | ng/mL | maximum observed drug concentration |
| t_{\max} | h | time of maximum observed drug concentration |
| $t_{1/2}$ | h | half-life associated with the terminal rate constant (λ_z) in non compartmental analysis (Week 8 dose only) |
| CL/F | L/h | apparent total body clearance of drug calculated after extra-vascular administration |
| V_z/F | L | apparent volume of distribution during the terminal phase after extra-vascular administration (Week 8 dose only) |
| RA | n/a | accumulation ratio based on AUC(0- τ) |
| Peak to trough | n/a | ratio of C_{\max} to C_{\min} (at 168 hours) |

Additional PK parameters may be calculated, as appropriate. The software and version used for the final analyses will be specified in the CSR. Any exceptions or special handling of data will be clearly documented within the final study report.

Formatting of tables, figures and abbreviations will follow the Eli Lilly Global PK/PD/TS Tool: NON-COMPARTMENTAL PHARMACOKINETIC STYLE GUIDE. The version of the tool effective at the time of PK analysis will be followed.

General PK Parameter Rules

- Actual sampling times will be used in the final analyses of individual PK parameters, except for non-bolus pre-dose sampling times which will be set to zero. For non-bolus, multiple dose profiles, the pre-dose time will be set to zero unless a time deviation falls outside of the protocol blood collection time window which is considered to impact PK parameter derivation.
- C_{\max} and t_{\max} will be reported from observed values. If C_{\max} occurs at more than one timepoint, t_{\max} will be assigned to the first occurrence of C_{\max} .
- AUC parameters will be calculated using a combination of the linear and logarithmic trapezoidal methods (linear-log trapezoidal rule). The linear trapezoidal method will be applied up to t_{\max} and then the logarithmic trapezoidal method will be used after t_{\max} . The minimum requirement for the calculation of AUC will be the inclusion of at least three consecutive plasma concentrations above the lower limit of quantification (LLOQ), with at least one of these concentrations following C_{\max} .
- $t_{1/2}$ will be calculated, when appropriate, based on the apparent terminal log-linear portion of the concentration-time curve. The start of the terminal elimination phase for each patient will be defined by visual inspection and generally will be the first point at which there is no systematic deviation from the log linear decline in plasma concentrations. $t_{1/2}$ will only be calculated when a reliable estimate for this parameter can be obtained comprising of at least 3 data points. If $t_{1/2}$ is estimated over a time window of less than 2

half-lives, the values will be flagged in the data listings. Any $t_{1/2}$ value excluded from summary statistics will be documented in the footnote of the summary table.

- A uniform weighting scheme will be used in the regression analysis of the terminal log-linear portion of the concentration-time curve.
- The parameters based on predicted C_{last} will be reported.

Individual PK Parameter Rules

- Only quantifiable concentrations will be used to calculate PK parameters with the exception of special handling of certain concentrations reported below the lower limit of quantitation (BQL). Plasma concentrations reported as BQL will be set to a value of zero when all of the following conditions are met:
 - The compound is non-endogenous.
 - The samples are from the initial dose period for a patient or from a subsequent dose period following a suitable wash-out period.
 - The timepoints occur before the first quantifiable concentration.
- All other BQL concentrations that do not meet the above criteria will be set to missing.

Individual Concentration vs. Time Profiles

- Individual concentrations will be plotted utilizing actual sampling times.
- The terminal point selections will be indicated on a semi-logarithmic plot.

Average Concentration vs. Time Profiles

- The average concentration profiles will be graphed using scheduled (nominal) sampling times.
- The average concentration profiles will be graphed using arithmetic average concentrations.
- The pre-dose average concentration for single-dose data from non-endogenous compounds will be set to zero. Otherwise, only quantifiable concentrations will be used to calculate average concentrations.
- Concentrations at a sampling time exceeding the sampling time window specified in the protocol, or $\pm 10\%$, will be excluded from the average concentration profiles.
- Concentrations excluded from the mean calculation will be documented in the final study report.
- A concentration average will be plotted for a given sampling time only if 2/3 of the individual data at the timepoint have quantifiable measurements that are within the

sampling time window specified in the protocol or $\pm 10\%$. An average concentration estimated with less than 2/3 but more than 3 data points may be displayed on the mean concentration plot if determined to be appropriate and will be documented within the final study report.

Treatment of Outliers during Pharmacokinetic Analysis

Application of this procedure to all PK analyses is not a requirement. Rather, this procedure provides justification for exclusion of data when scientifically appropriate. This procedure describes the methodology for identifying an individual value as an outlier for potential exclusion, but does not require that the value be excluded from analysis. The following methodology will not be used to exclude complete profiles from analysis.

Data within an Individual Profile

A value within an individual profile may be excluded from analysis if any of the following criteria are met:

- During the terminal elimination phase, the concentration is quantifiable and follows 2 consecutive concentrations that are BQL.
- For PK profiles during multiple dosing, the concentration of the pre-dose sample exceeds all measured concentrations for that individual in the subsequent post-dose samples.
- For PK profiles during single dosing of non endogenous compounds, the concentration in a pre-dose sample is quantifiable.
- For any questionable datum that does not satisfy the above criteria, the profile will be evaluated and results reported with and without the suspected datum.

Data between Individual Profiles

1. A value within an individual profile, (e.g. plasma concentrations obtained at the same point in identically treated individuals), may be excluded from analysis if it falls outside the range of acceptable values calculated as described in the methods below.

2. If $n < 6$, then the dataset is too small to conduct a reliable range test. Data will be analyzed with and without the atypical value, and both sets of results will be reported.

3. If $n \geq 6$, then an objective outlier test will be used to compare the atypical value to other values included in that calculation:

- a. Transform all values in the calculation to the logarithmic domain.
- b. Find the most extreme value from the arithmetic mean of the log transformed values and exclude that value from the dataset.
- c. Calculate the lower and upper bounds of the range defined by the arithmetic mean $\pm 3 \times \text{SD}$ of the remaining log-transformed values.

- d. If the extreme value is within the range of arithmetic mean $\pm 3*SD$, then it is not an outlier and will be retained in the dataset.
- e. If the extreme value is outside the range of arithmetic mean $\pm 3*SD$, then it is an outlier and will be excluded from analysis.

If the remaining dataset contains another atypical datum suspected to be an outlier and $n \geq 6$ following the exclusion, then repeat step 2 above. This evaluation may be repeated as many times as necessary, excluding only one suspected outlier in each iteration, until all data remaining in the dataset fall within the range of arithmetic mean $\pm 3*SD$ of the log-transformed values.

Reporting of Excluded Values

Individual values excluded as outliers will be documented in the final report. Approval of the final report will connote approval of the exclusion.

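### SAP 9.3.1 outlier test for six or more values: a flag is weak evidence of error at this study's group sizes, the exclusion wording conflicts, and no with-and-without report is required

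*SAP*

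**What the plan says.** SAP 9.3.1 opens its outlier rules permissively: "Application of this procedure to all PK analyses is not a requirement", and the procedure "does not require that the value be excluded from analysis".

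Under the sub-heading on data between individual profiles there are three numbered items.

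- Item 1 is permissive. A value, for example a concentration at one time point among identically treated patients, "may be excluded from analysis if it falls outside the range of acceptable values".
- Item 2 covers fewer than six values. The reason given is that "the dataset is too small to conduct a reliable range test", and the consequence is: "Data will be analyzed with and without the atypical value, and both sets of results will be reported".
- Item 3 covers six or more: "an objective outlier test will be used to compare the atypical value to other values included in that calculation". The values are logged, the most extreme one is set aside, and limits of 3 SD either side of the mean are computed from the rest. Step (e) then says of a value outside them: "then it is an outlier and will be excluded from analysis". The test may be repeated while at least six values remain, but the repeat instruction points to step 2, which is the rule for fewer than six.

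For a questionable value within one profile that meets none of the listed criteria, "the profile will be evaluated and results reported with and without the suspected datum". For item 3, the duty stated is to document excluded values in the final report.

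**The concern.** Three things come together in the branch for six or more values.

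- The multiplier is 3 at every n, although the limits come from a small set from which the most extreme value has already been removed. The cut-off is therefore tighter than a reader would take 3 SD to mean, and valid values can be flagged often.
- Step (e) is worded as an instruction to delete, while the preamble and item 1 leave deletion to judgement. Two analysts could treat the same flagged value differently and each cite the SAP.
- Paired results are asked for below six values because the test is unreliable there. From six upward they are not asked for, although the test is still far from reliable at six, eight or twelve.

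At stake is the between-patient spread in the PK summaries. A reader given only the reduced-data summary would have to recompute from the listings to see what the exclusion changed.

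**Working it through.** **Group sizes.** SAP 7 plans 12, 16 and 12 active patients, with 3 placebo patients in each cohort, and drop-out of 30%, 50% and 30%. This gives 15 × 0.70 + 19 × 0.50 + 15 × 0.70 = 30.5 completers, close to the stated figure of about 32. Applying the cohort rates to the active arms (an assumption) gives 12 × 0.70 = 8.4 and 16 × 0.50 = 8.0. If every drop-out were on active drug, 12 − 4.5 = 7.5 and 16 − 9.5 = 6.5 would remain. On either assumption the expected number is at least six. Early profiles can have up to 12 or 16 values.

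**Flag rate on clean data.** The SAP states no error rate. Assume normal log values and the usual sample SD. Setting one value aside, its distance from the mean of the others, divided by their SD times √(1 + 1/(n−1)), follows t with n−2 degrees of freedom. The chance that a set yields a flag is then close to

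n × P(|t(n−2)| > 3/√(1 + 1/(n−1))).

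| n | t cut-off | P per value | n × P | simulation (400,000 sets) |
|---|---|---|---|---|
| 6 | 2.74 | 0.0520 | 0.312 | 0.312 |
| 8 | 2.81 | 0.0309 | 0.247 | 0.246 |
| 12 | 2.87 | 0.0166 | 0.199 | 0.200 |
| 16 | 2.90 | 0.0115 | 0.185 | 0.182 |

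These rates are for one pass of the test on every set.

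**Where the limit lies.** For a value exactly at the limit, with s_full the SD of all n values and s_rest the SD of the other n−1,

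s_full²/s_rest² = (n−2)/(n−1) + 9/n.

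The value's distance from the full-set mean, in full-set SDs, is 3(n−1)/n divided by the square root of that ratio.

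| n | ratio | limit in full-set SDs | s_rest/s_full |
|---|---|---|---|
| 8 | 0.857 + 1.125 = 1.982 | 2.625/1.408 = 1.86 | 0.710 |
| 12 | 0.909 + 0.750 = 1.659 | 2.750/1.288 = 2.13 | 0.776 |
| 16 | 0.933 + 0.5625 = 1.496 | 2.8125/1.223 = 2.30 | 0.818 |

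A value further out makes the ratio larger. Any exclusion under the rule therefore cuts the log SD of the tested values by at least 29%, 22% or 18%, whatever the distribution.

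**Sensitivity to which values are tested.** The SAP does not define atypical. If only values beyond 2 full-set SDs are tested (an assumption), the flag rates are 12%, 20% and 18% at n = 8, 12 and 16. With a threshold of 2.5 SDs they are 3% at n = 12 and 8% at n = 16. At n = 8 that threshold cannot be reached by any value, valid or wrong, because the largest possible deviation is (n−1)/√n = 7/2.83 = 2.47 SDs. The 0% it gives there says nothing about reliability.

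**Sensitivity to shape.** If the log values had heavier tails (t with 5 degrees of freedom), the one-pass rates would be 36% to 39% at these four sizes.

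**The case against.** The strongest reply is that the preamble governs. It makes the procedure optional and says that a flagged value need not be removed, and item 1 agrees. Step (e) is then one loose verb at the end of an optional algorithm. This has force. A reader might infer from step (e) that the SAP makes deletion mandatory, and the section as a whole does not support that. What remains is a conflict of wording at the operative step.

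A reader might also take 18% to 25% as the expected share of sets that lose a valid value, or 25% as the worst case. Neither follows. The rates assume that every set is tested, whereas the SAP tests only a value already judged atypical and need not act on the flag. Nor is 25% a ceiling, since it is 31% at n = 6 and higher still with heavier tails.

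The fall in SD is an identity. It holds equally when a true assay error is removed, so it shows the size of the effect and not that the effect is wrong. That a flag is weak evidence rests on the clean-data flag rates.

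It would also go too far to say that exclusions are hidden or that the AUC and Cmax results are biased. Listings cover all patients and excluded values are documented. The SAP's example of a tested value is a concentration, and the effect on AUC or Cmax depends on how the profile is handled afterwards. The documents do not allow a figure for it.

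Finally, about eight per group is not the n for all PK data. The drop-out rates are per cohort and refer to completion on the planned regimen, while the PK population includes anyone dosed with evaluable data. A late dose-level group could fall below six, where paired results are already required.

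**Conclusion.** The point holds with limited reach. At the group sizes this study plans, the 3-SD rule flags clean log-normal sets often enough (about 25%, 20% and 18% at n = 8, 12 and 16 if every set were tested, and 31% at n = 6) that a flag alone is weak evidence of an error. How often valid values would actually be removed is unknown, because the SAP leaves both the choice of value and the decision to exclude to judgement. When a value is removed, the reported spread of the tested values falls by at least 18% to 29% over n = 16 down to n = 8.

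Step (e) contradicts the preamble and item 1. The SAP's own safeguard, reporting both results, stops at the sample size where this study's active groups begin. Only descriptive secondary PK summaries are affected; the primary adverse-event endpoint is not. The flag rates assume log-normal data and the sample SD, while the minimum fall in SD requires no distributional assumption.

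**What to change.** Reword step (e) along these lines: *If the extreme value is outside the range, it is flagged as an outlier and may be excluded when scientifically appropriate; results will be reported with and without any excluded value.* This brings the step into line with the preamble and item 1, and extends the SAP's reporting rule for fewer than six values to six or more. Correct the repeat instruction so that it points to step 3.

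The change is to SAP wording only. The cost is a few extra tables, and only when a value is excluded.

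Two further steps are open to choice and are not needed to resolve the point. One is to name the all-data result as the main one unless an assay or sampling cause is documented. The other is to let the multiplier depend on n; for a 5% flag rate per clean set it would be about 4.40, 3.86 and 3.68 at n = 8, 12 and 16. Statisticians could reasonably differ on both.

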9.3.2 Pharmacokinetic Statistical Methodology

PK parameters will be summarized using descriptive statistics by dose level.

PK dose proportionality may be assessed in an exploratory manner in model-based analysis performed by Eli Lilly.

9.4 Pharmacodynamic Assessment

9.4.1 Pharmacodynamic Analysis

The ability of LY3298176 to reduce fasting or dynamic glucose and the effects on insulin will be assessed. Such effects will be explored for different treatment regimens of LY3298176.

The following data will be summarized by treatment regimen and day, and listed:

- Fasting glucose concentrations
- Glucose concentrations and AUC(0-2h) during OGTT
- Insulin concentrations and AUC(0-2h) during OGTT
- Lipid panel (including high-density lipoprotein cholesterol, low-density lipoprotein cholesterol, total cholesterol, and triglycerides)
- Adiponectin concentrations (if available)
- Blood urea nitrogen concentrations
- Cortisol concentrations (if available)

- HbA1c concentrations
- 7-point glucose profile
- Markers of bone metabolism (if available)
- Meal intake and subjective rating of appetite sensation

The AUC(0-2h) for glucose and insulin during an OGTT will be calculated using the trapezoidal rule. The AUC(0-2h) as well as other derived parameters or observed concentration at specific timepoints for each patient on the study day will also be baseline-adjusted. The concentrations on Day 1, predose will be used as baseline.

9.4.2 Pharmacodynamic Statistical Methodology

Statistical inference on PD parameters (fasting blood glucose, OGTT glucose, and insulin) will be based on the patients who are included in the PD population. PD parameters may be transformed before statistical analyses, if deemed necessary.

The observed results, as well as change from baseline, will be analyzed by treatment regimen, using mixed-effects models to evaluate treatment effects, as well as treatment comparisons. The model will include treatment regimen actually received, as a fixed effect and the patient as a random effect. For repeated measured parameters, day and treatment regimen-by-day interaction terms will be included in the model. Baseline (Day -1) values, as well as other influencing variables, may be used as covariates. An unstructured covariance structure will be applied. If the model fails to converge, alternative structures shall be examined using Akaike's criteria. The main comparisons will be between each LY3298176-treated group and placebo group. Least-squares means as well as 95% CIs will be reported.

Example SAS code for repeated measures analysis:

```
proc mixed data=pd;
  class subject trtreg day;
  model chg = base trtreg day trtreg*day / residual ddfm=kr;
  repeated day / subject=subject type=un;
  lsmeans trtreg / alpha=0.05 cl pdiff;
  ods output lsmeans=lsm;
  ods output diffs=diff;
run;
```

where 'chg' is the change from baseline, 'base' is the baseline value, and 'trtreg' is the treatment regimen.

Example SAS code for mixed-effects analysis:

```
proc mixed data=pd;
  class subject trtreg;
  model pd = trtreg / residual ddfm=kr;
  random subject;
  lsmeans trtreg / alpha=0.05 cl pdiff;
  ods output lsmeans=lsm;
  ods output diffs=diff;
run;
```

where 'trtreg' is the treatment regimen.

The individual observed and mean (SD) time profile of the postdose PD parameters will be plotted by treatment regimen. Additional exploratory analyses of PD parameters may be performed to understand dose response using relevant model considering titration scheme, as deemed appropriate.

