Informed consent	X						
Distribution of glucose meters, test strips, and diaries/SMPG training	X ^e	X					
7-point SMPG		X ^f					
Medical history	X						
Physical examination	X						
Medical assessment	X			X	X	X	
AEs/concomitant medications	X			X	X	X	X
Chest x-ray ^g	X						
Height and weight	X						
Body temperature	X						
Vital signs (BP/PR) ^{h,i}	X			X	X	X	
12-Lead ECG ^{i,j}	X			X	X	X	
PK sampling ^{k,l}				X	X	X	X
Clinical safety lab (hematology, chemistry, urinalysis) ^{m,n}	X			X	X	X	
Clinical safety lab (serology) ⁿ	X						
Pregnancy test (serum, urine) ^{n,o,p}	X						
Follicle-stimulating hormone ^{n,o}	X						
Urine drug and alcohol screen ^{n,p}	X						
Hemoglobin A1c ^{l,m}	X						
Fasting glucose, insulin, glucagon ^{l,m}				X	X	X	
Immunogenicity ^l					X	X	X

Study Schedule Protocol I8F-JE-GPGC Cohort 1 for Treatment Period

Procedure	Treatment Period (Cohort 1)																					
	-1	1	2	3	4	8	15	16	17	18	22 ±1	29	30	31	32	36 ±1	43 ±1	50	51	52	57	ET1 ^d
Inpatient stay at CRU ^q	X	X	X	X	X		X	X	X	X		X	X	X	X		X	X	X			
Outpatient visits to CRU						X					X					X	X				X	X
Remind Patients about 7-point SMPG						X					X					X				X		
7-point SMPG							X					X					X				X	
Randomization		X																				
IMP administration ^r		X				X	X up-titra- tion				X	X up-titra- tion				X	X	X				
Medical assessments		Pre	X	X	X	X	X	X	X	X	X	X	X	X	X	X	X	X	X	X	X	
AEs/concomitant medications	X	X	X	X	X	X	X	X	X	X	X	X	X	X	X	X	X	X	X	X	X	
Weight ^t		Pre				Pre	Pre				Pre	Pre				Pre	Pre	Pre			X	X
Body temperature	X	Pre																				X
Vital signs (BP/PR) ^{h,i}	X	Pre, 1, 4, 8, 12	24	48	72	Pre	Pre	24	48	72	Pre	Pre	24	48	72	Pre	Pre	Pre			168	X
12-Lead ECG ^{i,j}		Pre, 8	24	48	72	Pre	Pre				Pre	Pre				Pre	Pre	Pre,	8	24	168	X
PK sampling ^{k,l}		Pre, 8	24	48	72	Pre	Pre				Pre	Pre				Pre	Pre	Pre,	8	24	48	168
Clinical safety lab (hematology, chemistry, urinalysis) ^{m,n}	X		24	48		Pre	Pre	24	48		Pre	Pre	24	48		Pre	Pre	Pre	24	48	168	X
OGTT ^{l,u}	X																			X		
Hemoglobin A1c ^{l,m}		Pre										Pre									168	X
Fasting glucose, insulin, glucagon ^{l,m}		Pre	24			Pre	Pre	24			Pre	Pre	24			Pre	Pre	Pre	24 ^v		168	X
Meal intake and appetite ^w	L/D		L/D																L/D			
Lipid panel ^{l,m,x}		Pre									Pre								24			X

Study Schedule Protocol I8F-JE-GPGC Cohort 1 for Treatment Period

Procedure	Treatment Period (Cohort 1)																				
	-1	1	2	3	4	8	15	16	17	18	22 ±1	29	30	31	32	36 ±1	43 ±1	50	51	52	57

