- m Patients will be required to fast for at least 8 hours before each blood sample is drawn.
- n These tests will be performed at the local laboratory.
- o These tests will be performed per investigator's discretion.
- p Procedures may be repeated throughout the study as deemed necessary by the investigator.
- q Patients may be required to remain at the CRU longer than the planned discharging day at the investigator's discretion to assure patients' safety or to provide additional safety monitoring.
- r IMP will be administered after an overnight fast of at least 8 hours. IMP must be administered at least 6 days after the previous dose.

- s Assessments of injection-site reactions will be included in the medical assessments.
- t Weight will be measured in a consistent way per Section 9.4.2.1, always predose.
- u OGTT (serum glucose and insulin) sampling schedule: Pre-glucose dose (75 g) and 0.5, 1, 1.5, and 2 hours post glucose dose. Patients should consume the glucose load within 5 minutes after an overnight fast of at least 10 hours.
- v Only insulin and glucagon will be measured at 24 hours postdose on Day 51. All other time points include fasting glucose.
- w Meal intake and subjective rating of appetite sensation will be evaluated before and 4 to 5 hours after standardized lunch and dinner meals on Days -1, 2, and 51. The standardized lunch and dinner meals will be provided at least 4 hours after the previous meal or the ingestion of glucose in the OGTT.
- x Lipid panel includes high-density lipoprotein cholesterol, low-density lipoprotein cholesterol, total cholesterol, and triglycerides. Triglyceride and total cholesterol concentrations in the safety panel will not be required on the days that the lipid panel is performed.
- y Exploratory storage samples may be assayed for biomarkers like adiponectin, cortisol, and bone biomarkers. Refer to Section 9.6.2 for details.

3. Introduction

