8. DEFINITION OF ANALYSIS POPULATIONS

The “Safety” population will consist of all enrolled patients, whether or not they completed all protocol requirements.

The “Pharmacokinetic” population will consist of all patients who received at least one dose of IMP and have evaluable PK data.

The “Pharmacodynamic” population will consist of all patients who received at least one dose of IMP and have evaluable PD data.

Patients treated with placebo will be pooled for PD and safety analyses.

All protocol deviations that occur during the study will be considered for their severity/impact and will be taken into consideration when patients are assigned to analysis populations.

Additional analyses will be conducted on the basis of the treatment groups defined by titration regimen as actually treated, if deemed necessary, after data review.

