9.5.4 Vital signs

Vital signs data will be summarized by treatment regimen together with changes from baseline, where baseline is defined as Day 1, predose. Figures of mean vital signs and mean changes from baseline profiles will be presented by treatment regimen. Furthermore, values for individual patients will be listed.

For change from baseline in vital signs, a mixed-model repeated-measure model with treatment regimen, time (of measurement), and treatment regimen-by-time interaction as fixed effects, patient as random effect, and baseline as covariate will be used to determine the effects of LY3298176. An unstructured covariance structure will be applied. If the model fails to converge, alternative structures shall be examined using Akaike's criteria. Least-squares means, as well as 95% CIs, will be reported.

Example SAS code:

```
proc mixed data=safety;
  class subject trtreg day;
  model chg=trtreg day trtreg*day base / residual ddfm=kr;
  repeated day / subject=subject type=un;
  lsmeans trtreg*day / alpha=0.05 cl pdiff;
  ods output lsmeans=lsmeans;
  ods output diff=diffs;
run;
```

where 'chg' is the change from baseline, 'base' is the baseline value, and 'trtreg' is the treatment regimen.

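### The example repeated-measures code in SAP 9.4.2 requests only day-averaged LS means; on the fasting-glucose schedule these are non-estimable for all three LY3298176 regimens, so it should request them by day

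*SAP*

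**What the plan says.** SAP 9.4.2 covers inference on fasting glucose and the OGTT measures. It groups patients by regimen received: "The model will include treatment regimen actually received, as a fixed effect and the patient as a random effect". It then adds the time terms: "For repeated measured parameters, day and treatment regimen-by-day interaction terms will be included in the model". The target is stated as "The main comparisons will be between each LY3298176-treated group and placebo group", with LS means and 95% CIs to be reported. The text does not say whether those LS means are per day or averaged over days, nor which days enter the model. In the repeated-measures example code the only LS-means request is "lsmeans trtreg / alpha=0.05 cl pdiff".

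The vital-signs model in SAP 9.5.4 has the same fixed effects, but its code requests "lsmeans trtreg*day / alpha=0.05 cl pdiff".

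On placebo, SAP section 8 states: "Patients treated with placebo will be pooled for PD and safety analyses". Protocol section 2 sets the sampling days cohort by cohort, and footnote v adds: "Only insulin and glucagon will be measured at 24 hours postdose on Day 51. All other time points include fasting glucose".

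**The concern.** With the interaction in the model, an LS mean for regimen alone is the unweighted average of that regimen's cell means over every day level in the data. If a regimen was never sampled on one of those days, that cell mean has no data behind it and the average cannot be estimated. Here the extra samples taken 24 hours after an up-titration (Days 16, 30 and 44) are scheduled only in the cohorts that up-titrate at that time, so gaps are built into the design.

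At stake is the model-based comparison of each LY3298176 regimen with placebo on fasting glucose. Run literally, the line returns no estimate for it. The repair would then be chosen with data in hand, and the candidates (dropping days, dropping the interaction, reporting by day) answer different questions.

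**Working it through.** **Inputs.** Post-baseline fasting-glucose days from the Schedule of Activities (Protocol section 2), leaving out Day 1 (baseline) and Day 51 (no glucose, footnote v), and including follow-up Days 64 and 85:

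- Cohort 1 (2.5–10 mg): 2, 8, 15, 16, 22, 29, 30, 36, 43, 50, 57, 64, 85
- Cohort 2 (5–15 mg): 2, 8, 15, 16, 22, 29, 36, 43, 44, 50, 57, 64, 85
- Cohort 3 (5 mg): 2, 8, 15, 22, 29, 36, 43, 50, 57, 64, 85

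The Cohort 3 Day 50 entry is lost in the text extraction of that table and is restored from the Appendix 7 count. The result does not depend on it, since without it there would be one more empty cell. Planned numbers (SAP section 7) are 12, 16 and 12 on LY3298176, with 3 placebo patients per cohort.

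**Check against the plan's own count.** Adding back Days 1 and 51 gives 13 + 2 = 15 samples for Cohorts 1 and 2 and 11 + 2 = 13 for Cohort 3. Protocol Appendix 7 gives 15 and 13 for fasting plasma glucose and insulin, so the schedule has been read correctly.

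**Empty cells.** The cohorts together use 14 distinct days, so there are 4 regimens × 14 = 56 cells. Pooled placebo has data on all 14 days. The LY3298176 gaps are:

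| Regimen | Days with no sample | Days sampled |
|---|---|---|
| 2.5–10 mg | 44 | 13 |
| 5–15 mg | 30 | 13 |
| 5 mg | 16, 30, 44 | 11 |

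That is 1 + 1 + 3 = 5 empty cells and 51 filled.

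**Estimability.** Write μ(r,d) for the mean of regimen r on day d. The request as written targets (1/14) Σ μ(r,d), and the difference (1/14) Σ [μ(r,d) − μ(placebo,d)]. Each μ(r,d) is a free parameter under the interaction, so any empty cell enters with weight 1/14 and no information. A formal check used the fixed-effects matrix X (intercept, baseline, regimen, day, regimen-by-day): a linear function L is estimable only if adding L as a row leaves the rank of X unchanged.

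- Day-averaged LS mean: estimable for placebo, not estimable for any of the three LY3298176 regimens.
- Day-averaged difference from placebo: 0 of 3 estimable.
- Per-day differences: 13 + 13 + 11 = 37 of 3 × 14 = 42 estimable.
- Average over the 11 days shared by all cohorts: estimable for all three regimens.

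**Variations.**

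- Stopping at Day 57 (12 days, 48 cells) leaves the same 5 gaps and the same result.
- Fasting insulin, if modelled this way, adds Day 51 in every cohort: 15 days, 60 cells, the same 5 gaps, and 45 − 5 = 40 per-day differences estimable.
- If Cohort 2 patients held at 5 mg are regrouped under 5 mg as the regimen received, the gaps fall to 3. The 5 mg group still lacks Day 30, so all three averages remain non-estimable.

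**Precision by day after the change.** At planned enrolment there are 9 placebo patients on the 11 shared days, 6 on Day 16, and 3 on each of Days 30 and 44. With equal variances and no within-patient correlation, the standard-error ratios are:

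- 2.5–10 mg, Day 30 to Day 29: √[(1/12 + 1/3)/(1/12 + 1/9)] = 1.46
- 5–15 mg, Day 44 to Day 43: √[(1/16 + 1/3)/(1/16 + 1/9)] = 1.51

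With compound symmetry and correlation 0.9, generalised least squares gives 1.06 and 1.07, because placebo patients from the other cohorts then contribute through their neighbouring days.

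**The case against.** The block is labelled as example code, and the SAP text never asks for a day average. The trial has no a priori statistical requirement, its primary endpoint is adverse events, and SAP 9.4.1 already summarises glucose by regimen and day. A non-estimable LS mean announces itself and cannot produce a wrong number unnoticed. The TFL shells, which are not among the documents supplied, may specify by-day contrasts. The content of the analysis dataset is also undefined, and if it held only the 11 shared days the line would run as it stands.

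All of this limits the harm, but none of it makes the line correct. In the supplied text the example is the only indication of which LS mean is intended, nothing restricts the days, and the by-day summaries are descriptive rather than model-based comparisons. The fallback to other covariance structures does not help, because estimability is fixed by the fixed-effects design.

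One further point stands but is separate. An unstructured covariance over 14 days has 14 × 15/2 = 105 parameters for 49 patients, and Days 30 and 44 are never observed in the same patient, so their covariance is not identified. Changing the LS-means line neither causes nor cures this; the analysis would rely on the SAP's fallback to a simpler structure. It is also fair to say that 37 per-day differences do not by themselves single out a main comparison.

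**Conclusion.** The concern holds. On the scheduled fasting-glucose days, the example line gives 0 of 3 LY3298176 LS means and 0 of 3 differences from placebo for the only secondary PD endpoint. This rests on two assumptions: days enter the model under nominal labels, and all scheduled days are included, which the SAP does not restrict. It does not depend on drop-out, on the covariance structure or on whether follow-up days are included. The standard-error ratios additionally assume full planned enrolment, equal variances and compound symmetry. The line should be corrected, but the damage is confined to one illustrative statement: the fixed-effects model already supports the by-day contrasts, and the safety conclusions are untouched.

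**What to change.** In the SAP 9.4.2 repeated-measures example, change the LS-means effect from regimen to regimen by day, as in SAP 9.5.4, and add a sentence saying that LY3298176–placebo differences with 95% CIs are reported within each day. The same sentence can name the day or days of main interest. Keep all scheduled days in the model, including Days 64 and 85, and footnote that the Day 30 and Day 44 differences rest on 3 placebo patients at planned enrolment.

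If a single averaged contrast is also wanted, define it over the 11 shared days (2, 8, 15, 22, 29, 36, 43, 50, 57, 64, 85) and state that it averages over titration doses and post-treatment follow-up. If the TFL shells already specify by-day contrasts, only the example line needs aligning.

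The cost is one line of code and one sentence, and no data leave the model. The downside is that 3 contrasts become up to 37, which should be read as exploratory. The five empty cells stay non-estimable, as they should.
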